We have experience evaluating AB in smokers using RT tasks. For example, in one study we examined whether AB to smoking words, as measured by the smoking Stroop task, was associated with the motivational salience of smoking pictures, as measured by peripheral physiology [58]. Scores for the smoking Stroop and for the peripheral physiology, including zygomaticus major ("smile muscle") electromyography (EMG), corrugator supercilii ("frown muscle") EMG, heart rate (HR) and skin conductance (SC), were created by taking a difference score for each measure by subtracting the responses to the neutral from the smoking stimuli. Smokers who had slower RTs to smoking words produced larger zygomaticus major EMG to smoking cues than those with faster RTs. However, scores on the smoking Stroop were unrelated to the corrugator supercilii EMG, HR, or SC responses to smoking stimuli. These results suggest that AB to smoking cues is more strongly associated with appetitive motivational measures (i.e., zygomaticus major activity) than with measures of avoidance (i.e., corrugator supercilii activity) or measures of physiological arousal (i.e., HR, SC). This is consistent with theories that smoking cues are associated with conditioned responses that capture attention, and are consistent with other work from our lab [59,60].

We have experience assessing in-home AB in smokers trying to quit. As part of an Ecological Momentary Assessment (EMA) study, we had 119 community smokers carry around a personal data assistant (PDA) during the first week following their scheduled quit attempts [61]. As part of multiple planned and random assessments per day, participants recorded their craving to smoke and completed a modified Stroop task, a measure of AB to smoking words. Overall, the smokers produced a significant smoking Stroop effect, (17.9 ms, $SD=46.6$; $t[118]=4.19$, $p<.0001$, Cohen's $d = 0.38$), indicating AB to smoking words, and the smoking Stroop effect was positively correlated with craving ratings, $r(117)=.28$, $p<.01$. These results demonstrate that reliable and significant AB can be captured on a hand-held device in a participant's day-to-day environment, and that this AB is associated with self-reported craving.

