We have used ERPs, including the P1, as a reliable measure of AB in smokers. We evaluated ERP differences among picture categories using randomization tests on time regions of interest identified by temporal principal component analysis [23]. We found that both emotional and cigarette-related pictures prompted significantly more positivity than did neutral pictures over central, parietal, and frontal sites in the 452-508 ms time window. During the 212-316 ms time window, both pleasant and cigarette-related pictures prompted less positivity than neutral images did. However, only cigarette-related pictures, and not the emotional pictures (pleasant and unpleasant), significantly enhanced the amplitude of the P1 component (136-144 ms) relative to neutral conditions. These results demonstrate that, for smokers, cigarette-related cues uniquely capture attentional resources very early during visual processing and engage brain circuits normally involved in the processing of intrinsically motivationally relevant stimuli.

Figure 2: Study event diagram, relative to the baseline laboratory session.

Lab Session	Day	Study Event
1	1	Baseline Lab Session, 1-day pre-training
	2 ... 14	Daily In-Home ABM training and AB assessment ... Daily In-Home ABM training and AB assessment
2	15	Follow-up Lab Session; Given NRT
	16	Begin NRT; Quit Smoking
	29	Taking NRT; Phone counseling
	43	Taking NRT; Phone counseling
	57	Taking NRT; Phone counseling
3	72	Stop NRT; Follow-up Lab Session

D. RESEARCH DESIGN AND METHOD

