Baseline laboratory session: Final eligibility. Participants will be instructed to smoke ad lib prior to their baseline lab session. At the baseline, which will occur within 30 days of the telephone screen, participants will have their smoking status assessed, as a final determinant of eligibility, using expired CO or the NicAlert strip. To determine eligibility with the Major Depression and suicidality criteria, participants will complete the Patient Health Questionnaire-9 (PHQ-9), a reliable and valid self-administered diagnostic instrument that assesses depression severity and risk for suicide [62,63]. Additionally, the subject will be assessed for interest in providing a genetic sample according to procedures described in our IRB-approved genetic banking protocol (Protocol # Lab 09-0099). Any individual who is deemed ineligible for study participation due to the PHQ-9 will be assessed by a master's level counselor and will be given referral recommendations for local psychiatric resources (see "Project SmartMod Mental Health Procedures" in the Appendix, for details). Urine will be collected and tested to evaluate eligibility on the drug use and pregnancy criteria, and participants will be considered ineligible if they are pregnant or have a positive toxicology screen for any of the following drugs: cocaine, opiates, methadone, benzodiazepines, barbiturates, amphetamines, methamphetamines, PCP, or THC. Final eligibility will be determined by the PI, [name], a licensed and credentialed psychologist, and his designated study staff members.

Laboratory sessions: Smoking behavior assessment. Prior to each of the 3 lab sessions, participants may be sent a link to complete the visit questionnaires via email. At each of the 3 lab sessions, participants will provide an expired CO sample, a urine sample to measure cotinine (a tobacco metabolite that measures nicotine exposure) and anabasine (a tobacco metabolite that will allow us to distinguish NRT use from smoking [64]), and complete TLFB [65] to record CPD for the prior seven days at visit 1 and CPD since last visit for visits 2, 3 and each of the telephone counseling sessions. Next, if not previously completed, participants will complete a computerized battery of questionnaires related to smoking behavior. Nicotine

[figure not shown]

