In-Home Smartphone: Assessments of Smoking and Craving. At the start of the ABM training, the smartphone will be used to assess daily cigarette consumption and cigarette craving. Participants will be asked to provide the number of cigarettes smoked so far on the day of the assessment, the time that they smoked their most recent cigarette, and a rating of their current “urge” to smoke on a scale from 0 (no urge) to 9 (maximum urge). This single-item measure of craving has been previously used in ecological momentary assessment studies and has been shown to be both reliable and valid (e.g., predictive of subsequent smoking) [111,112]. Additionally, participants will also be asked to provide the amount of caffeine and alcohol that has been consumed each day. Importantly, this assessment will only take about 1 minute to complete, which will minimize burden and allow the participants to immediately proceed to the ABM training.

In-Home Smartphone: Assessment of Training Environment. We will use the smartphone to assess characteristics of the training environment. This will allow us to explore possible relationships between environmental distractions and performance, and also serve as a measure of compliance regarding the instruction to complete the task in a quiet, well-lit location. Throughout the ABM training and assessment period, the smartphone will sample the ambient lighting, background noise levels in dB (no sounds or video will be recorded), and motion (using an accelerometer reading) every 30 s. If the tri-axial accelerometer detects excessive motion, the task will automatically pause at the end of the next block and a message will be displayed reminding the participant to hold the phone still when completing the task. When the motion subsides, the task will resume and the block during which excessive motion was detected will be repeated.

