
Statistical Approach & Expected Outcomes

Aim 1. Identify the impact of in-home ABM on AB. We will evaluate this aim using 2 (group: ABM vs. sham) X 3 (session: baseline, 1-day post-training, and 8-weeks post-training) linear mixed model using RT difference scores (neutral-cigarette) as the dependent measures and subject as the random effect. We will conduct separate analyses on the dependent measures (within-modality: MDP RT difference scores; between-modality: Stroop RT difference scores) collected at baseline, 1-day post-training, and 8-weeks post-training. We predict that post-training AB scores, calculated from RT, will decrease from baseline for those in the ABM training, but not in the sham training condition, indicating a reduction in AB to smoking cues.

Aim 2. Identify the impact of in-home ABM on smoking behavior. We will evaluate this aim using two types of models. For the continuous (i.e., normally distributed) measures of smoking behavior, we will conduct mixed between-within repeated measures ANOVA using the same predictors and covariates as are described in Aim 1. Separate analyses will be run for each of the continuous dependent measures, including mean CPD over the past 7 days, expired CO, cotinine, FTND, and WSWS Craving. We expect that ABM training, compared to sham training, will decrease measures of smoking exposure (CPD, expired CO, cotinine), levels of dependence (FTND), and levels of craving (WSWS Craving) at the 1-day and 8-weeks post-training sessions. For the categorical variable of 8-weeks post-NRT abstinence, we will conduct a chi-square test of independence on the 2 (abstinent vs. nonabstinent) x 2 (ABM vs. sham training) table. We expect that ABM training, compared to sham training, will result in a higher rate of abstinence.

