Exploratory analyses. We will examine the Aim 1 and 2 models covarying the total number of completed ABM or sham training sessions, the number of in-home training sessions completed, in-home training sessions accuracy rates, baseline FTCD, sex at birth, and CPD at each session. We will conduct the following exploratory analyses using multilevel modeling: (1) We will examine the impact of ABM on AB, CPD, and craving assessments collected by smartphone to determine whether the optimal length of training is less than 13 days; (2) We will examine whether individual differences, measured at baseline, predict response to the ABM training on our measures of AB and smoking behavior. These individual differences will include baseline levels of nicotine dependence (i.e., FTND, mCEQ, CPT, and WSWS), mood (i.e., PANAS), anhedonia (i.e., SLIPS), impulsivity (i.e., DDT, SUPPS-P), tolerance to stressors (i.e., DTS and ASI), reward sensitivity (i.e., Passive Picture Viewing), smoking exposure (i.e., CPD and expired CO), gender, handedness (i.e. Chapman Handedness questionnaire), and AB to smoking cues; (3) We will examine whether participants' contingency awareness of the ABM task influenced ABM's effectiveness, because one ABM study with smokers found that only those participants who were aware of the relationship between the probe and stimulus type were responsive to ABM [7]; (4) We will use data about the training environment collected using the smartphone (e.g., location, dB levels, ambient lighting) to examine whether these environmental characteristics influenced ABM's effectiveness; (5) We will use the EEG data collected using our 129-channel sensor net to perform event-related potential (ERP) analyses (including the P1 component), along with source localization analysis to attempt to identify areas in brain that are responsive to ABM. We will preliminarily target occipital regions that have been found to activate in the presence of motivationally salient visual cues [91,124]. (6) We will examine the effects of AB on eye-tracking metrics (e.g., fixation, gaze duration) and compare the reliability of eye tracking with traditional reaction time metrics of AB.

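### The exploratory re-runs of the Aim 1 and 2 continuous-outcome models adjust for CPD at each session, a post-randomization Aim 2 outcome, so the adjusted ABM term is not a total treatment effect and is not labelled as anything else

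*Combined protocol and SAP*

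**What the plan says.** All references are to the combined protocol and SAP.

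- **Statistical Approach & Expected Outcomes, Exploratory analyses.** The Aim 1 and 2 models are to be examined with added covariates: training sessions completed, then "in-home training sessions accuracy rates, baseline FTCD, sex at birth, and CPD at each session". The dependence score is marked as a baseline value; CPD is not. No outcome is exempted, and the adjusted term is not described as direct, mediated or mechanistic.
- **Same section, Aim 1.** The main model is a 2 (group) "X 3 (session: baseline, 1-day post-training, and 8-weeks post-training) linear mixed model". No covariates are listed.
- **Same section, Aim 2.** The continuous outcomes are modelled separately, "including mean CPD over the past 7 days, expired CO, cotinine, FTND, and WSWS Craving". The plan predicts that ABM "will decrease measures of smoking exposure (CPD, expired CO, cotinine), levels of dependence (FTND), and levels of craving (WSWS Craving") at both post-training sessions.
- **Laboratory sessions: Smoking behavior assessment.** The timeline follow-back (TLFB) records "CPD for the prior seven days at visit 1 and CPD since last visit for visits 2, 3" and at each counseling call.
- **Figure 2.** Training runs on days 2 to 14, visit 2 is on day 15, and visit 3 ("Stop NRT; Follow-up Lab Session") is on day 72.
- **In-Home Smartphone: Assessments of Smoking and Craving.** The phone asks for "the number of cigarettes smoked so far on the day of the assessment".

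**The concern.** A covariate measured after randomization, and expected to respond to treatment, does not sharpen the estimate of the treatment effect. It changes what is estimated. Holding CPD fixed removes whatever part of the ABM effect runs through smoking. It also lets in bias from anything that drives both CPD and the outcome.

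The plan's own hypothesis makes CPD such a variable, and the instruction covers the model in which CPD is the dependent variable. An ABM term that shrinks or disappears after adjustment could be reported as a weaker treatment effect, when it only reflects conditioning on one of the treatment's intended results. What is at stake is the reading of the exploratory tables.

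**Working it through.** **1. The plan's detectable effect (Power analysis).** Inputs: N = 250, two groups, m = 3 sessions, alpha 0.01, within-subject correlation 0.5, epsilon 0.75, f = 0.11.

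- Noncentrality = f² × N × m × epsilon / (1 − 0.5) = 0.0121 × 250 × 3 × 0.75 / 0.5 = 13.61.
- Degrees of freedom: (2−1)(3−1)(0.75) = 1.5 and (250−2)(3−1)(0.75) = 372.
- Power at f = 0.11 is 82.1%. Power of 80% is reached at f = 0.1077, which rounds to the stated 0.11. With 30% attrition (N = 175) the value is 0.1290, against the stated 0.13.

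Both figures reproduce. The calculation has no covariate term, so it describes the unadjusted interaction.

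**2. The same effect in SD units.** Suppose the group difference is 0 at baseline and d at visits 2 and 3. The interaction effects per cell are then d/3, d/6 and d/6 in absolute size. Their mean square is (d²/9 + d²/36 + d²/36)/3 = d²/18, so f = d/√18 and d = 0.11 × 4.243 = 0.467 SD.

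**3. Outcomes other than CPD.** Standardize outcome and CPD, and let r be their correlation, taken as equal within and between persons (an assumption). The coefficient on session CPD is then about r, so

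adjusted effect ≈ outcome effect − r × CPD effect.

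The share removed is r × (CPD effect / outcome effect). With both effects set to −0.467 SD (an assumption):

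| r | Adjusted, by formula | Share removed | Simulated visit 3 term, unadjusted → adjusted |
|---|---|---|---|
| 0 | −0.467 | 0% | −0.469 → −0.469 |
| 0.28 | −0.336 | 28% | −0.462 → −0.331 |
| 0.50 | −0.234 | 50% | −0.463 → −0.229 |
| 0.70 | −0.140 | 70% | −0.468 → −0.137 |

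The simulation used a random-intercept model with 125 per arm, complete data and 1,000 trials per row. A separate run with both effects at −0.30 SD gave −0.30 → −0.21 (r = 0.3), −0.30 → −0.15 (r = 0.5) and −0.32 → −0.10 (r = 0.7). With no ABM effect on CPD and r = 0.5 it gave −0.30 → −0.30. The two terms therefore agree only if r or the CPD effect is zero. A negative r enlarges the term: at r = −0.28, −0.468 → −0.601.

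**4. CPD as the outcome.**

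- *Covariate and outcome are the same seven-day mean.* The model fits itself: the CPD coefficient is 1, every group-by-session term is 0, and 100% of the effect is removed.
- *Covariate is CPD since the last visit.* On the scheduled days it equals the outcome at visit 1. It contains the outcome at visit 2 (7 of 14 days) and, if the window runs from visit 2, at visit 3 (7 of 57 days, days 15 to 71). A constant effect shifts covariate and outcome equally, and the coefficient is close to 1, so little is left.

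The second case was simulated from daily CPD with an assumed constant effect of −2 per day. Other assumptions were person SD 5, a quit drop of mean 9 and SD 4, and a range of daily autocorrelation and drift. The share removed was 92–107% at visit 2 and 98–117% at visit 3. It was smaller at visit 3 under other assumptions: 69–80% if the effect grows from −1 to −3, 70–86% in a quit-and-relapse process, and 84% or 49% with recall error of SD 3 or 6 in the covariate alone. The visit 3 figures assume the 57-day window.

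**5. If in-home sessions were meant.** Those counts are part-day and exist only on training days, so they give no value at visits 1 or 3. A per-person summary over the training period could be used, but it would still be post-randomization.

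**The case against.** **Only exploratory output is affected.** The sentence sits under an exploratory heading and never calls the adjusted term a treatment effect. The unadjusted models are specified separately, and asking whether an effect persists at a given level of smoking is a legitimate question. This stands and sets the severity. It does not remove the need to say what the adjusted term estimates.

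**"Session" is ambiguous.** The other uses in that sentence refer to training sessions. This stands in part. On the in-home reading the overlap with the Aim 2 CPD outcome in step 4 falls away, but the covariate remains post-randomization.

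**The visit 3 window is not fixed.** TLFB is also taken at the calls on days 29, 43 and 57. Study overview speaks of the last contact for make-up visits and allows late visits. A reader might infer that adjustment would reverse the sign of the ABM effect on CPD. The documents do not support that: it needs a fading effect together with an assumed 57-day window, and with a window starting at the last call the reversal nearly disappears.

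**The correlations are assumed.** This also stands. The documents give no correlation of AB with CPD. The 0.28 under Preliminary Studies relates Stroop bias to craving and serves here only as one point in a range. A reader might infer a specific loss in milliseconds for Aim 1, but nothing in the documents allows that calculation.

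**Conclusion.** The point holds, and it is minor. As written, the exploratory re-run with CPD as the outcome is uninformative: a constant effect is essentially all removed, and exactly all if covariate and outcome are the same variable. For the other continuous outcomes, the adjusted ABM term differs from the total effect by about r times the CPD effect. That is 28% to 70% of the effect for r from 0.28 to 0.70 when both effects are 0.467 SD, and nothing when r or the CPD effect is zero. These sizes rest on assumed correlations, effects and complete data; the formula itself does not depend on the particular values.

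A reader might infer that the trial's main results are compromised. They are not. The Aim 1 and 2 models list no CPD covariate, the abstinence chi-square has no covariates, and the power figures reproduce for the unadjusted interaction. The statement under Potential Problems & Alternative Strategies that compliance and accuracy will enter the aim models is a separate matter. It should be reconciled with the covariate lists on its own terms.

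**What to change.** In Exploratory analyses:

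1. Replace CPD at each session with baseline (visit 1) CPD, or delete it.
2. Drop it from the model in which CPD is the outcome.
3. If post-baseline CPD is kept in any model, define its window. Label that model mechanistic (direct effect), not a treatment-effect estimate, and state that it assumes no unmeasured common causes of CPD and the outcome.

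The cost is a few lines of wording. Visit 1 CPD is already collected, and no new data or change in sample size is needed. With complete data, baseline CPD as a main effect leaves the group-by-session term unchanged, so deletion serves that term equally well.

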Study overview. Participants will be 250 community smokers, currently interested in quitting smoking, who will be randomly assigned (stratified by gender) to receive either ABM or sham training. Smokers in both groups will attend three laboratory sessions (Figure 2). The first lab session will establish each smoker's baseline smoking behavior and AB towards smoking picture and word cues by assessing reaction time (RT) and event-related potential (ERP) electroencephalography to modified dot-probe (MDP), Stroop color-word naming tasks and a passive picture viewing task. After the first lab session, participants will complete 13 days of daily in-home training (ABM or sham) and AB assessments that will be administered through a provided smartphone, with compliance and accuracy rewarded monetarily. The second lab session will occur the day after the final day of in-home training and will involve the same assessments as the first session, to gauge the short-term impact of ABM on AB and smoking behavior. At the end of the second lab session, participants will have a 30-minute counseling session with a smoking cessation counselor and be given the first half of an 8-week supply of NRT. The participants will be instructed to quit the next day, and will have 3 biweekly phone counseling sessions while on NRT. After participants complete one biweekly phone counseling session, they will be mailed the remainder of their 8-week supply of NRT. Participants will be given a window of seven days after the scheduled date of their second lab session to complete the session. The final lab session, which will occur 8 weeks after the second session, will measure the longer-term impact of training on smoking behavior and AB. Participants will be given a window of fourteen days after the scheduled date of their final lab session to complete the session. Out of window visits will be noted in the progress notes but will not be considered a protocol deviation. Visit 3 has a window with an ending period of whenever final abstinence data is collected or the trial ends, whichever is sooner. A study staff member will make attempts to contact participants who miss Visit 3 until the end of the study or until the participant requests no further efforts be made to contact them. For those who miss Visit 3, a study staff member will call them to invite them to come in as originally planned so that abstinence (e.g., TLFB assessment since last contact, CO, urine cotinine, and anabasine), and lab data can be collected. If participants are unable to attend Visit 3, staff will ask participants to complete TLFB over the telephone to record CPD since last visit. Staff also will offer to send participants' questionnaires via email. If smoking abstinence is reported, staff will invite participants to come in or will offer to send them a NicAlert or comparable urine cotinine test to biochemically verify abstinence. Participants will be asked to send a picture of the cotinine test to research staff via text message, email, or postal mail.

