Power analysis. To demonstrate that this proposal has adequate sample size to detect meaningful amplitude changes in the continuous measures taken at the post-training laboratory sessions (Specific Aims 1 & 2), we conducted a power analysis using the G*Power program (v3.1.2; Heinrich Heine University, Düsseldorf, Germany). We calculated power to ensure that we could detect a significant 2-way (ABM intervention by time) ANOVA interaction for any of our continuous measures, as assessed at the baseline, 1-day post-training, and 8-weeks post-training sessions. If we assume a conservative Bonferroni-corrected Type I error rate of $\alpha=0.01$, 250 participants, moderately correlated within-subject observations ($r=0.5$), and a conservative nonsphericity correction ($\varepsilon=0.75$) we have 80% power to detect differences corresponding to a Cohen's f of 0.11 or larger for the 2-way interaction. Even if we were to experience an unlikely 30% attrition rate, we would have power to detect a Cohen's f of 0.13 or larger. According to Cohen [117], a Cohen's f of 0.10, 0.25, and 0.40 correspond to a small, medium, and large effect size, respectively, meaning that we have the power to detect a small effect size or greater on our continuous measures. To demonstrate that we would have adequate power to detect likely AB differences for Aim 1, we searched the literature for studies with a similar design to ours. Given that no previous study has evaluated the impact of multi-session ABM on AB in

smokers, we decided to estimate a likely effect size from the one alcohol study that used the MDP task for both multi-session ABM and the AB assessments [2]. We estimated a Cohen's *f* value for this study by taking the square root of the *F* ratio multiplied by the ratio of the degrees of freedom [117]. From this formula, we estimated a Cohen's *f* of 0.64, based on the reported *F* value for the significant ABM training group (ABM, sham) main effect, $F(1,23)=9.4$, $p<.01$. This Cohen's *f* value corresponds to a large effect size and is well within the range for which we have sufficient power to detect. We recognize that this alcohol study does not provide an ideal comparison for the effects sizes we will likely obtain, but it does suggest that ABM produces large effects on AB, effects which should be well within the power requirements of our study to detect.

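### The power statement claims sensitivity to a small effect, but the plan's own detectable effects (f = 0.11 and 0.13) lie above its own value for small (f = 0.10)

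*Combined protocol and SAP*

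**What the plan says.** The statement is in the combined protocol and SAP, section D, under Power analysis. The calculation concerns the interaction of training group with time for any of the continuous measures in Aims 1 and 2. It was done in G*Power with 250 participants, a Bonferroni-corrected alpha of 0.01, a within-subject correlation of 0.5 and a nonsphericity correction of 0.75.

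Four statements follow one another:

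1. With 250 participants there is 80% power for f of 0.11 or larger.
2. "Even if we were to experience an unlikely 30% attrition rate, we would have power to detect a Cohen's f of 0.13 or larger".
3. Citing Cohen, "a Cohen's f of 0.10, 0.25, and 0.40 correspond to a small, medium, and large effect size, respectively".
4. The conclusion drawn from these: "meaning that we have the power to detect a small effect size or greater on our continuous measures".

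The design behind the calculation is given under Statistical Approach, Aim 1: a two-group by three-session model, with sessions at baseline, one day after training and eight weeks after training. The Study overview gives two arms, "randomly assigned (stratified by gender) to receive either ABM or sham training".

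**The concern.** Statement 4 does not follow from statements 1 to 3. The plan ties small to a single value, 0.10, and a claim that covers small effects and anything greater includes that value. Yet the smallest effects for which power is stated are 0.11 and 0.13. The mismatch can be seen without calculation. What needs checking is whether it is only rounding and, if not, how much power the design has at 0.10.

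At stake is how accurately the document describes its own sensitivity. The sentence covers every continuous outcome in Aims 1 and 2, and a reader who takes only the conclusion would credit the design with a property that its inputs do not give it.

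**Working it through.** **Inputs.** From Power analysis: alpha = 0.01, N = 250, correlation r = 0.5, nonsphericity correction e = 0.75, target power 80%, attrition 30%. From Aim 1: k = 2 groups and m = 3 sessions. Equal allocation is assumed; the description of randomisation gives no ratio. With 30% attrition, N = 250 × 0.70 = 175.

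**Formula.** This is the G*Power default for a within-between interaction in a repeated measures ANOVA, a noncentral F test with

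- noncentrality L = f² × N × m × e / (1 − r)
- df1 = (k − 1)(m − 1)e = 1 × 2 × 0.75 = 1.5
- df2 = (N − k)(m − 1)e = 248 × 1.5 = 372 for N = 250, and 173 × 1.5 = 259.5 for N = 175

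**Step 1: reproduce the plan's figures.** Solving for f at 80% power:

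| Analysed N | Detectable f, computed | Plan states | Power at the stated f |
|---|---|---|---|
| 250 | 0.1077 | 0.11 | 82.1% |
| 175 | 0.1290 | 0.13 | 80.8% |

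Both agree after rounding. Among the variants tried (no nonsphericity correction, the correction left out of the noncentrality, alpha of 0.05, and effect-size conventions that do not use r), none at alpha 0.01 gives both printed values. The default form is therefore very likely the one the plan used.

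**Step 2: is it only rounding?** No. Before rounding, 0.1077 and 0.1290 are still above 0.10.

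**Step 3: power at f = 0.10.**

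- N = 250: L = 0.01 × 250 × 3 × 0.75 / 0.5 = 11.25, power **72.2%**
- N = 175: L = 0.01 × 175 × 3 × 0.75 / 0.5 = 7.875, power **51.8%**

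For scale, 80% power at f = 0.10 needs about 290 analysed participants, or 290 / 0.70 = about 415 enrolled at 30% attrition. This measures the gap; it is not a proposal to enlarge the trial.

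**Step 4: sensitivity to the plan's assumptions.** Power at f = 0.10, changing one input at a time:

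| Inputs | N = 250 | N = 175 |
|---|---|---|
| As stated (r = 0.5, e = 0.75) | 72% | 52% |
| r = 0.4 | 62% | 42% |
| r = 0.6 | 84% | 64% |
| e = 1 (no correction) | 83% | 64% |

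**Step 5: optional translation to SD units.** This needs an assumed pattern of the arm difference over the three sessions, which the plan does not give.

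- Equal difference d at both post-training sessions, (0, d, d): f = d / √18, so d = 4.243f. Then 0.1077 gives 0.46 SD and 0.1290 gives 0.55 SD.
- Difference halved at one of the two sessions, (0, d, d/2) or (0, d/2, d): f = d / √24, so d = 4.899f. Then the larger of the two differences is 0.53 SD and 0.63 SD.

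**The case against.** The strongest reply is that nothing is concealed and little is wrong. The detectable effects are correct, and they stand beside the benchmarks, so any reader can see that 0.11 is not 0.10. On a loose reading, 0.11 and 0.13 belong to the small range, far below the medium value of 0.25, where power exceeds 99.9% at either sample size. The plan calls both its alpha and its nonsphericity correction conservative. A single common correlation with equal variances would imply sphericity, and without the correction the detectable f at N = 250 is 0.097, so the claim would hold at full sample. Finally, 30% attrition is described as unlikely, and N = 175 treats every dropout as wholly lost, whereas the Aim 1 mixed model can keep earlier sessions from people who miss the last one.

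Much of this stands. The calculation is sound, the full-sample gap is 0.0077 in f, and 52% is a lower figure that should carry its assumption. Two parts do not stand. The plan equates small with 0.10, so the loose band is not its own definition. Dropping the correction, or raising the correlation to 0.6, replaces the plan's stated inputs with more favourable ones; a correlation of 0.4 would move power the other way, to 62%. Even with the correction dropped, the claim fails at N = 175 (64%).

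A reader might go further and infer that the trial is powered only for half-SD effects that the label hides, or that a null result will be taken to exclude small effects. The documents support neither. They state no SD target, and the SD figures change with the assumed pattern over sessions. They also contain no rule that reads a null result in that way, and the adequacy argument for Aim 1 leans on an anticipated f of 0.64 from an alcohol study, with its limits as a comparison acknowledged.

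**Conclusion.** The concern holds as an overstated conclusion. By the plan's own definition and inputs, the study does not have 80% power for a small effect: power at f = 0.10 is about 72% with all 250 analysed, and about 52% with 175 if dropouts contribute nothing. The result rests on the stated alpha, correlation and nonsphericity correction, on equal allocation, and on the G*Power default form, which reproduces both printed detectable effects.

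It is tempting to conclude that the sample size calculation is wrong, or that the trial must be enlarged. Neither follows: the detectable effects are right as printed, and nothing in the documents commits the trial to detecting exactly f = 0.10. The shortfall is modest at full sample and large only in the attrition case that the plan considers unlikely.

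**What to change.** Replace the concluding sentence with wording such as: *80% power for f of at least 0.108 (N = 250) or 0.129 (30% attrition), slightly above Cohen's small effect of 0.10, for which power is about 72% and 52%.* Drop the claim of power for a small effect, and note that the attrition figures assume no data from dropouts.

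A translation into SD units is optional. If one is added, state the assumed pattern over sessions with it, for example about 0.46 and 0.55 SD when the arm difference is equal at both post-training sessions.

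The cost is a slightly less favourable statement of sensitivity. No change to sample size, alpha, model or outcomes is needed.
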